3.2.2. Lost to Follow Up

A participant will be considered lost to follow-up if he or she repeatedly fails to return for scheduled visits and is unable to be contacted by the study site.

If a participant fails to return to the clinic for Visit 2 or Visit 3, the site should attempt to contact the participant (where possible, 3 telephone calls and, if necessary, a certified letter to the participant's last known mailing address or local equivalent methods) and reschedule the missed visit as soon as possible. If a participant is completely unreachable, they are considered to have withdrawn from the study with a primary reason of lost to follow-up.

3.3. Study Population

This study plans to enrol 460 patients with symptomatic COPD (details in sample size estimation in [Section 3.7](#)). In this study, patients will be recruited from approximately 30 centres in China. The study sites will be selected from different regions and tiers of hospitals around China to ensure the patients could be representative. Based on local market research data, the proportion of participants with different baseline maintenance treatments in this study may be adjusted during enrolment stage to reflect the real-world status of COPD maintenance treatment pattern in China.

3.4. Eligibility Criteria

3.4.1. Inclusion Criteria

AGE
1. Participant must be 40 years or above of age inclusive, at the time of signing the informed consent.
TYPE OF PARTICIPANT AND DISEASE CHARACTERISTICS
2. Participants with a documented physician diagnosis of COPD;

3. CAT \geq 10;
4. Existing COPD Maintenance Treatment. Patients currently receiving one of the maintenance therapies listed below with no minimum treatment duration prior to screening (Visit 1):
 - ICS/LABA (single or multiple inhalers)
 - LAMA/LABA (single or multiple inhalers)
 - Free combination of ICS, LAMA, LABA
5. Current or former cigarette smokers with a history of cigarette smoking history \geq 10 pack-years at screening.
6. Trelegy is prescribed under the discretion of clinical physicians with medical records providing documentation of a Trelegy prescription in daily practice.

INFORMED CONSENT

7. Capable of giving signed informed consent which includes compliance with the requirements and restrictions listed in the informed consent form (ICF) and in this protocol.

3.4.2. Exclusion Criteria

Women of childbearing potential

1. Women who are pregnant or lactating or are planning on becoming pregnant during the study.

PRIOR/CONCOMITANT THERAPY

2. Treated with Trelegy within 3 months prior to screening (Visit 1).
3. Patients who, in the opinion of the treating investigator, are chronic users of oral corticosteroids for respiratory or other indications (if unsure discuss with the medical monitor prior to screening). Chronic use is defined as more than 14 days' continuous use during the 12 weeks prior to Visit 1.

MEDICAL CONDITIONS

4. Patients with any life-threatening condition i.e. low probability, in the opinion of the investigator, of 3-month survival due to severity of COPD or comorbid condition.

MEDICAL CONDITIONS

5. Patients with unstable COPD. Patients with resolution of an exacerbation less than 2 weeks prior to Visit 1. Patients may be rescreened 2 weeks after resolution of exacerbation (exacerbation is defined as: requiring treatment with antibiotics and/or systemic steroids or hospitalisation; resolution is defined as: 2 weeks after all symptoms have resolved and any medicines to treat the exacerbation have finished).
6. Patients who need more than 3 L/min supplemental oxygen at rest at screening.
7. Other diseases/abnormalities: Patients with historical or current evidence of uncontrolled or clinically significant disease. Significant is defined as any disease that, in the opinion of the investigator, would put the safety of the participant at risk through participation, or which would affect the efficacy or safety analysis if the disease/condition exacerbated during the study.

PRIOR/CONCURRENT CLINICAL STUDY EXPERIENCE

8. Participation received any investigational drug in other clinical trial within four weeks or 5 half-lives prior to this study whichever is longer.

OTHER EXCLUSIONS

9. Any conditions or illnesses listed in the section of contraindications in the Summary of Product Characteristics (SmPC) of Trelegy, i.e., hypersensitivity to the active substances of Trelegy Ellipta;
10. Inability to read: In the opinion of the Investigator, any participant who is unable to read and/or would not be able to complete study related materials.

3.5. Treatment**3.5.1. Treatment Administered**

All patients will receive Trelegy (FF/UME/CVI ELLIPTA 100/62.5/25 µg) according to the local SmPC. Participants are expected to inhale one dose in the morning from the Trelegy Ellipta at approximately the same time each day for 12 weeks after enrolment.

3.5.2. Concomitant Therapy

Any medication or vaccine for the treatment of a respiratory condition that the participant receives at the time of consent or receives during the study should be recorded along with:

- dates of administration including start and end dates
- dosage information including dose and frequency

3.6. Study Assessments and Procedures

3.6.1. Effectiveness Assessments

3.6.1.1. The COPD Assessment Test (CAT)

The COPD Assessment Test (CAT) is a validated 8-item questionnaire developed for use in routine clinical practice to measure the health status of patients with COPD [Jones, 2009; Jones, 2012]. Participants rate their experience on a 6-point scale (Protocol 8.1 Appendix 1-1), ranging from 0 (no impairment) to 5 (maximum impairment) with a scoring range of 0-40. Higher scores indicated greater disease impact.

The questionnaire is completed on paper prior to the study treatment and before any procedures or assessments are performed (to avoid influencing the participant's response). To avoid biasing responses, the participant is not to be told the results of any diagnostic tests prior to completing the CAT questionnaire. Questionnaires are to be administered at Visit 1, Visit 2 and Visit 3/E.D.

A change of 2 unit compared to baseline is considered as the MCID [Jones, 2012].

3.6.1.2. Modified Medical Research Council (mMRC)

The mMRC was developed in 1960 [Behrman S, 1960], and it's considered adequate for assessment of symptoms, as it relates well to other measures of health status and predicts future mortality risk [GOLD, 2021].

The mMRC (Patient Version and Physician Version) will be used to assess the breathlessness state of the patient before and after the treatment (Protocol 8.2 Appendix 1-2). With it, patients are scored on a scale of 0-4 depending on their disability due to shortness of breath from 0 (no impact) to 4 (worst possible impact).

The mMRC (Patient Version) will be completed by each patient firstly, without supervision, after CAT. The investigator should check whether the patient has completed the mMRC adequately but cannot assist in completing it. Then, the investigators will finish the mMRC (Physician Version) through their observation.

3.6.1.3. **Pulmonary function test (spirometry) for Pre-dose FEV₁, FVC, FEF₂₅₋₇₅, IC**

Pre-dose FEV₁, FVC, FEF₂₅₋₇₅ and IC are all measured through a pulmonary function test (spirometry). Pre-dose FEV₁ and FVC are basic items of COPD's pulmonary function test (PFT). FEV % of predicted value is a good indicator to assess moderate to severe airflow limitation [GOLD, 2021]. It's used clinically as a predictor of exacerbation or mortality in patients with COPD [CMA, 2018]. FEF₂₅₋₇₅ is one of the standard results provided in spirometry reports too, low FEF₂₅₋₇₅ is well known indicator of small airway obstruction [GOLD, 2021]. IC is measured as you exhale casually followed by a maximal inhalation. The calculation for IC is tidal volume plus inspiratory reserve volume. The decrease of IC is associated with an increase at the end of expiration, it can be used as a simple assessment of lung volume changes in COPD [GOLD, 2021].

Spirometry for assessment of pulmonary function is to be performed as described in [Table 1](#) in all participants at Visit 1 and Visit 3/E.D.

All sites will use their own spirometry equipments for pulmonary function test. For Pre-dose FEV₁, FVC, FEF₂₅₋₇₅ and IC determination, at least 3 acceptable spirometry efforts (no more than 8) need to be obtained. To facilitate pre-dose spirometry, participants are encouraged to time their COPD maintenance therapy so that they are due for their next dose at the time of the study visit, which should be in the morning.

Each spirometry should be performed prior to the day's dose of usual care/ study treatment. The largest Pre-dose FEV₁, FVC, FEF₂₅₋₇₅ and IC from the 3 acceptable efforts are recorded, even if not from the same effort. If it is not possible to withhold usual care/study treatment and/or short-acting beta-agonists or anti-cholinergic for ≥ 4 hours, spirometry is still measured and recorded along with the most recent use of COPD maintenance treatment/ study treatment.

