3.7.2 Sample size consideration

A sample size of 460 is planned. With the aforementioned assumptions in [Table 1](#), the sample size would be able to provide a half-width ranging from 0.64 to 0.73 for the 95% confidence interval (CI) of the inverse probability weighted mean of the change from baseline in CAT score at week 12 in the primary analysis under different missingness scenarios ([Table 3](#)).

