2. STATISTICAL HYPOTHESES

The primary objective of this study is to evaluate the effectiveness following 12-week treatment with Trelegy by comparison to baseline data. There are no formal hypothesis tests associated with this objective and no formal significance tests.

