4.4. Exploratory Endpoints Analyses

The analysis approaches for the below exploratory endpoints are analogous to the primary analysis and the sensitivity analyses for the primary endpoint:

- Change from baseline of Forced Vital Capacity (FVC) at week 12
- Change from baseline of Forced Expiratory Flow at the 25% and 75% (FEF_{25-75}) at week 12
- Change from baseline of Inspiratory Capacity (IC) at week 12

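### Recording the largest FEF25-75 from any effort tends to favour less complete blows in slow-emptying patients, so this exploratory change can shift with effort length between visits (minor)

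*Protocol*

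**What the plan says.** Protocol 3.6.1.3 asks for a set number of efforts per session: "at least 3 acceptable spirometry efforts (no more than 8) need to be obtained". It then records the largest FEV1, FVC, FEF25-75 and IC "from the 3 acceptable efforts are recorded, even if not from the same effort". FEF25-75 may therefore come from a different blow than the recorded FVC.

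On equipment it says: "All sites will use their own spirometry equipments for pulmonary function test". Section 3.3 plans approximately 30 centres. The protocol does not define an acceptable effort, and it gives no minimum expiratory time or end-of-test criterion. Under Table 1, note 4, only the four spirometry values are entered in the eCRF. Expiratory time and the FVC of the effort that supplied FEF25-75 are not listed.

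The protocol gives FEF25-75 a specific meaning: a low value "is well known indicator of small airway obstruction". SAP 4.4 lists its week 12 change as an exploratory endpoint and says: "The analysis approaches for the below exploratory endpoints are analogous to the primary analysis and the sensitivity analyses for the primary endpoint". It names no adjustment for volume or effort length.

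**The concern.** For FEV1 and FVC, a larger value within a session indicates a better effort, so taking the maximum is sensible. FEF25-75 behaves differently, because its measuring window is set by the FVC of the same blow. If a slow-emptying patient stops early, FVC falls, the window moves to the earlier and faster part of the curve, and FEF25-75 rises although the lungs are unchanged.

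If practice or coaching makes blows longer, or more uniform, at Visit 3 than at Visit 1, the recorded FEF25-75 changes with no change in the airways. The single cohort has no comparator from which to subtract this, and the data listed for collection would not reveal it. One recorded artefact could also move FVC up while FEF25-75 goes down.

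**Working it through.** **The plan's own figures.** The documents give no figure for FEF25-75. The sample-size figures concern CAT only: 1.96 × 7.003 / √460 = 0.640, which agrees with the stated half-width of 0.64. Nothing below affects it.

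**Inputs.** From the documents: three acceptable efforts, the largest-value rule, and the same rule at both visits. Assumed, because the documents are silent: the shape of the volume curve, the effort lengths, and the blow-to-blow noise.

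**Formula.** For a volume curve V(t) cut off at time T, FVC = V(T). FEF25-75 = 0.5 × FVC / (t75 − t25), where t25 and t75 are the times at which 25% and 75% of that FVC have been exhaled.

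**Step 1: one unchanged slow-emptying lung.** V(t) = 0.9(1 − e^(−t/0.35)) + 1.6(1 − e^(−t/3.0)) litres.

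- T = 5 s: FVC 2.198 L, t25 0.229 s, t75 1.906 s; 0.5 × 2.198 / 1.677 = 0.655 L/s.
- T = 10 s: FVC 2.443 L, t25 0.264 s, t75 2.624 s; 0.5 × 2.443 / 2.360 = 0.518 L/s.
- T = 6 s and T = 8 s give 0.603 and 0.545 L/s.

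FEV1 is 1.302 L throughout. The 5 s blow reads roughly a quarter higher than the 10 s blow.

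**Step 2: change between visits with no true change.** Three efforts per session, uniform effort lengths, 3% scaling noise, 200,000 simulated patients per visit. Visit 1 efforts last 5-10 s and Visit 3 efforts 8-10 s, except in the second row.

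| Assumed curve | Largest FEF25-75 | Effort with largest FEV1+FVC |
|---|---|---|
| Slow two-compartment (Step 1) | 0.602 to 0.545 L/s: −0.058 (−9.6%) | 0.560 to 0.542 L/s: −0.019 (−3.3%) |
| Same curve, 6-10 s then 7-10 s | −3.2% | −1.1% |
| Single compartment, tau 2 s | −3.4% | −1.3% |
| Faster two-compartment (1.2 L, tau 0.4 s; 1.3 L, tau 1.5 s) | about −1% | −0.8% |
| Single compartment, tau 1 s | −0.2% | −0.2% |

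With 5-10 s efforts at both visits, the mean change is zero under either rule.

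**Step 3: how often the shortest blow is chosen.** Chance is 33%. On the slow curve the largest-value rule picks the shortest blow in 82% of 5-10 s sessions and 52% of 8-10 s sessions. For the tau 1 s curve it is 36% and 34%.

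**Step 4: a second set of assumptions.** Two-compartment curve of 3.0 L (45% with tau 0.5 s, the rest with tau 4 s), effort length mean 8 s and SD 1.5 s, 3% noise.

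- Mean length moving to 7, 9 or 10 s at Visit 3 gives +9.0%, −6.7% or −11.7% under the protocol rule, against +4.9%, −3.8% or −6.7% under the FEV1+FVC rule.
- Mean length unchanged but SD falling from 1.5 to 0.5 s gives −6.5% against +2.2%.

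**Step 5: mixing rules within a participant.** On the Step 1 curve, with identical 5-10 s efforts at both visits, Visit 1 under the largest-value rule and Visit 3 under the FEV1+FVC rule gives 0.560 − 0.602 = −0.042 L/s, about −7%.

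**The case against.** The case for leaving the rule alone has real weight.

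- The same rule applies at both visits, so a stable selection effect cancels in the change. This stands: the artefact needs a shift in effort length or variability, and the documents give no evidence of one.
- FEF25-75 depends on effort length under any rule. This also stands: in Step 4 the protocol rule nearly doubles the dependence but does not create it, and the alternative leaves part of it.
- The size depends on curves and effort lengths that the documents do not supply, and it is close to nothing for fast-emptying lungs. Acceptability may also be defined in site instructions outside the public documents.
- The endpoint is exploratory. Of the primary objective the SAP says: "There are no formal hypothesis tests associated with this objective and no formal significance tests". Protocol section 4 already acknowledges the lack of a control group.
- A rule change in mid-study can itself cause a false change (Step 5). This is correct, and it shapes the fix.

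A reader might infer that the rule always selects the least complete expiration. That holds only if the efforts differ in length alone; with noise it is a tendency. A reader might also infer that the artefact flatters the product. The documents do not support that: blows that lengthen with practice would produce a false worsening.

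**Conclusion.** The point holds as a minor one. The rule is stated explicitly, nothing in the protocol or SAP limits or adjusts for effort length, and the direction follows from the definition of FEF25-75. Under the main scenario the false change lies between about −0.2% and about −10%, depending on how slowly the lungs empty, and it is zero when effort lengths match across visits. The other assumed curve and shifts in Step 4 reach −11.7% and +9.0%.

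These are illustrations under assumed curves and effort lengths, not forecasts. It would be wrong to conclude that the trial will report a spurious 10% change, or that its main results are in doubt. One exploratory endpoint is concerned; CAT, FEV1, the planned 460 participants and the precision figures are untouched. The label in SAP 4.4, "Change from baseline of Forced Expiratory Flow at the 25% and 75"%, describes a mean flow between two points as a flow at those points. That is a clerical matter and affects no computation.

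**What to change.** In Protocol 3.6.1.3, keep the largest-value rule for FEV1 and FVC. Record FEF25-75 from the single acceptable effort with the largest sum of FEV1 and FVC, and state this in SAP 4.4.

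Apply one rule to both visits of a participant. Where Visit 1 was recorded under the present rule and can be re-extracted, re-extract it. Where it cannot, either keep the present rule for that participant's Visit 3, or report those pairs separately and descriptively. If no values can be re-extracted, leave the rule as it is and report FEF25-75 descriptively with a caveat about effort length. A stated end-of-test criterion, with expiratory time and FVC of the chosen effort recorded, would address part of what remains; this is optional for an exploratory endpoint.

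Cost: no extra manoeuvre, a short text change, slightly lower absolute FEF25-75 values (0.560 against 0.602 L/s for 5-10 s efforts on the slow curve), and re-extraction work across approximately 30 sites. The protocol does not say whether the values of each effort are kept, so feasibility has to be checked with the sites first.

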3.6.2 Safety Assessments

The following safety events will be collected during the study:

- All Trelegy related AEs
- All SAEs
- AEs that lead to the discontinuation of Trelegy

COPD exacerbation is a disease-related event. Because exacerbations are typically associated with the disease under study, an exacerbation will not to be reported as an SAE unless, in the investigator's opinion, the event is of greater intensity, frequency, or duration than expected for the individual participant, or the investigator considered that there is a reasonable possibility that event is related to study treatment.

The investigator or site staff are responsible for detecting, documenting and reporting events that meet the definition of an AE or SAE. The following information on AEs will be obtained:

- Patient's coded data
- Treatment's data
- Reporter's data
- Duration (start and stop dates).
- Severity (mild, moderate, severe).
- Causality (reasonable possibility yes/no).
- Actions taken and outcome.

The detailed definitions and procedures for recording, evaluating, follow-up, and reporting of the AEs, study treatment related AEs and SAEs are listed in [APPENDIX 3](#).

3.6.2.1 Physical examination

A complete physical examination will include, at a minimum, assessments of the Cardiovascular, Respiratory, Gastrointestinal and Neurological systems. Height and weight will also be measured and recorded.

Investigators should pay special attention to clinical signs related to previous serious illnesses.

3.6.2.2 Vital signs

Vital signs (Body Temperature, Pulse Rate, Blood Pressure) will be performed at the time points specified in Visit 1 and Visit 3/E.D. prior to conducting spirometry and prior to taking the morning dose of study treatment. Blood pressure (systolic and diastolic) and pulse rate will be measured in the sitting position after approximately 5 minutes rest. A single set of values will be collected and recorded in the source documentation and eCRF.

3.6.2.3 Oxygen saturation

The oxygen saturation of participants is evaluated by pulse oximetry, to ensure whether they need supplemental oxygen or not. Patients who need more than 3 L/min supplemental oxygen at rest at screening are excluded.

3.6.2.4 Electrocardiogram

12-lead resting ECG will be conducted at Visit 1. All ECG measurements will be made with the participant in a supine position having rested in this position for approximately 5 minutes before each reading. The investigator or a designee will evaluate whether the ECG is normal or abnormal. ECGs may be repeated for quality reasons . Dated and signed printouts of ECG with findings should be documented in patient's medical record.

3.7 Sample Size Calculations

3.7.1 Statistical assumptions

INTREPID study [study 206854 China CSR GSK Document Number [2019N418769_00](#)] showed that in the real world setting 19% participants had early withdrawn from the Trelegy treatment prior to week 24. Considering the difference in the China clinical practice and study designs, it is assumed that 79% enrolled participants would complete 12 weeks of Trelegy treatment with no intercurrent events, 20% would have the intercurrent event of receiving a new COPD maintenance therapy, 1% would have the intercurrent event of treatment discontinuation.

Based on results from a few studies, i.e., IMPACT [[Lipson](#), 2018; study CTT116855 China CSR GSK Document Number [2018N356723_00](#)], INTREPID [study 206854 China CSR GSK Document Number [2019N418769_00](#)] and one randomized controlled trial (RCT) [[Bansal](#), 2021], it is assumed that a decrease of 2 in the primary endpoint at week 12 will be observed in this study with a common standard deviation of 7 ([Table 2](#)).

Table 2 Assumptions for the primary endpoint

Proportion of each type of participants	Primary endpoint		
	Mean	Standard deviation	
Participants with no intercurrent events	79%	-2	7
Participants receiving other COPD maintenance therapy	20%	-2	7
Participants with treatment discontinuation	1%	0	7
Total	100%	-1.98	7.003

3.7.2 Sample size consideration

A sample size of 460 is planned. With the aforementioned assumptions in [Table 1](#), the sample size would be able to provide a half-width ranging from 0.64 to 0.73 for the 95% confidence interval (CI) of the inverse probability weighted mean of the change from baseline in CAT score at week 12 in the primary analysis under different missingness scenarios ([Table 3](#)).

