4.2.2. Main analytical approach

Primary analysis will be conducted using an inverse-probability weighted mixed model for repeated measures (MMRM) for the change from baseline in CAT score under the missing at random (MAR) assumption to handle missingness which may occur during the data collection.

The inverse probability weighting (IPW) method can reduce the selection bias caused by the missingness, by weighting the participants whose change from baseline of CAT score is observed at week 12 using the inverse probability of completeness in the endpoint. The key assumption for the IPW method is MAR which means that the missingness mechanism of the primary endpoint could be modelled using the observed factors, i.e. the baseline covariates and the post-baseline covariates by the time of missingness, and no unmeasured confounders are involved in the missingness mechanism.

To estimate the probability of the completeness of the primary endpoint, a logistic model is constructed to model its missingness mechanism with the missingness status as the dependent variable (status=observed, status=missing as the reference group). The following baseline and post-baseline covariates will be considered for the missingness of change from baseline in CAT score at week 12:

- Age,
- Gender,
- Years of COPD,
- Smoking history: smoking status and number of pack years,
- Pre-dose FEV1 at baseline,
- COPD maintenance treatment at baseline,
- CAT score at baseline,
- The change from baseline in CAT score at week 4,
- Intercurrent event status: no intercurrent events, received other COPD maintenance therapy, Trelegy discontinued due to other reason.
The subjects receiving other COPD maintenance therapy are those who have discontinued their Trelegy therapy and switched to other COPD maintenance therapy.
- Duration of Trelegy

The right tail of estimated weights may be truncated by its appropriate percentile if deemed necessary.

The change from baseline in CAT score will be analysed using the MMRM model with the covariates of smoking status, CAT score at baseline, visit, the interaction of CAT score at baseline*visit, in which each observation is weighted with the inverse probabilities derived from the above logistic regression models.

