5. SAMPLE SIZE DETERMINATION

INTREPID study [study 206854 China CSR GSK Document Number [2019N418769_00](#)] showed that in the real world setting 19% participants had early withdrawn from the Trelegy treatment prior to week 24. Considering the difference in the China clinical practice and study designs, it is assumed that 79% enrolled participants would complete 12 weeks of Trelegy treatment with no intercurrent events, 20% would have the intercurrent event of receiving a new COPD maintenance therapy, 1% would have the intercurrent event of treatment discontinuation.

Based on results from a few studies, i.e., IMPACT [[Lipson](#), 2018; study CTT116855 China CSR GSK Document Number [2018N356723_00](#)], INTREPID [study 206854 China CSR GSK Document Number [2019N418769_00](#)] and one randomized controlled trial (RCT) [[Bansal](#),

2021], it is assumed that a decrease of 2 in the primary endpoint at week 12 will be observed in this study with a common standard deviation of 7.

A sample size of 460 is planned. With the assumptions in Table 1 of the protocol, the sample size would be able to provide a half-width ranging from 0.64 to 0.73 for the 95% confidence interval (CI) of the inverse probability weighted mean of the change from baseline in CAT score at week 12 in the primary analysis under different missingness scenarios.

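### The stated half-width of 0.64–0.73 assumes 460 independent participants, and no site-level variance is specified for a single-arm mean taken from about 30 centres

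*Protocol*

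**What the plan says.** **Precision.** Protocol 3.7.2 states "A sample size of 460 is planned" and that "the sample size would be able to provide a half-width ranging from 0.64 to 0.73 for the 95% confidence interval (CI". SAP 5 repeats "a half-width ranging from 0.64 to 0.73 for the 95% confidence interval (CI) of the inverse probability weighted mean". Protocol 3.7.1 assumes that the CAT change "will be observed in this study with a common standard deviation of 7". Tables 3 and 4 vary the sample size, the standard deviation and the missingness. Neither table varies correlation within sites.

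**Sites.** Protocol 3.3 says "patients will be recruited from approximately 30 centres in China". It adds that sites come from different regions and hospital tiers, so that the patients are representative.

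**Analysis.** Under SAP 4.2.2 the change in CAT is "analysed using the MMRM model with the covariates of smoking status, CAT score at baseline, visit" and the baseline-by-visit interaction, with inverse-probability weights. The covariates listed for the weight models do not include site. The sensitivity MMRM (SAP 4.2.3) has the same covariates and names no site factor for the imputation. SAP 4.3 and 4.4 follow the primary analysis by analogy. Neither document specifies a site random effect, a clustered variance or a site-level bootstrap. Neither states how the standard error of the weighted MMRM is obtained.

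**Inference.** SAP 2 states that there are no formal hypothesis tests. The sample size is justified by interval width alone.

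**The concern.** The result of this study is a mean change in one treated cohort. In a trial randomised within sites, a site effect shared by both arms largely cancels from the contrast. Here nothing cancels it, so between-site variance in the change enters the variance of the estimate in full.

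Such variation is plausible. Treating physicians decide whom to switch, the study is open label, CAT is a paper questionnaire, and the sites are chosen to differ. An MMRM models correlation between visits of the same participant. A default model-based standard error, or a robust one clustered on participant, would both treat two participants at the same hospital as unrelated.

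The 95% confidence interval is the study's only inferential output. If site variation exists, that interval is too narrow, and the planned precision is better than the design can deliver.

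**Working it through.** **Inputs from the documents.** N = 460 and SD = 7. Group shares are 79% (no intercurrent event), 20% (other maintenance therapy) and 1% (discontinuation), with mean changes -2, -2 and 0, so the overall mean is -1.98 (Protocol 3.7.1, Table 2). Missingness by group is 0/0/0% in Scenario 1, 5/30/50% in Scenario 2 and 10/50/70% in Scenario 3 (Table 3). About 30 sites gives 460/30 = 15.3 participants per site.

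**Assumptions.** The ICC of CAT change within site is not given, so 0, 0.01, 0.02 and 0.05 are used. Sites are of equal size unless stated.

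**Step 1: reproduce the plan's figure.** Weighting inflates the variance by f = Σ p/(1 - m), where p is a group's share and m its missing proportion:
- Scenario 1: f = 1
- Scenario 2: f = 0.79/0.95 + 0.20/0.70 + 0.01/0.50 = 1.137
- Scenario 3: f = 0.79/0.90 + 0.20/0.50 + 0.01/0.30 = 1.311

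The spread of the group means adds 0.99 × 0.02² + 0.01 × 1.98² = 0.0396. With independent participants the half-width is 1.960 × √[(49f + 0.0396)/460], which gives 0.640, 0.682 and 0.733. The protocol prints 0.64, 0.69 and 0.73. The ends match, and Scenario 2 differs by about 1%. The other rows of Tables 3 and 4 agree to within 0.01 (for example 0.786 against a printed 0.78 at N = 400, Scenario 3). The stated range therefore contains no site component.

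**Step 2: add a site component.**

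Variance = 49 × [ICC/30 + (1 - ICC) × f/460] + 0.0396/460

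Example, ICC 0.02, Scenario 3: 49 × [0.000667 + 0.98 × 1.311/460] + 0.000086 = 0.1696, so SE = 0.412. The half-width is 1.960 × 0.412 = 0.807 with the normal quantile and 2.045 × 0.412 = 0.842 with t on 29 degrees of freedom.

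**Step 3: coverage if site is ignored.** Coverage ≈ 2Φ(1.960 × SE at ICC 0 / SE at the assumed ICC) - 1.

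| Assumed ICC | Half-width, normal (Scenario 1 to 3) | Half-width, t on 29 df (Scenario 1 to 3) | Coverage of unadjusted 95% CI |
|---|---|---|---|
| 0 | 0.640–0.733 | 0.668–0.765 | 95% |
| 0.01 | 0.684–0.771 | 0.714–0.804 | 93–94% |
| 0.02 | 0.726–0.807 | 0.757–0.842 | 92–93% |
| 0.05 | 0.838–0.908 | 0.875–0.947 | 87–89% |

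**Step 4: unequal sites.** With no missingness the design effect is 1 + ICC × [15.3 × (1 + CV²) - 1], where CV is the coefficient of variation of site size. For an assumed CV of 0.7 it is 1.22, 1.44 and 2.09 at ICC 0.01, 0.02 and 0.05. Coverage, 2Φ(1.960/√design effect) - 1, is then about 92%, 90% and 83%. In simulations with unequal sites, a site-clustered standard error with t on (sites - 1) degrees of freedom covered about 94%. At ICC 0 it widened the interval by about 2%.

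**Step 5: does it change the reading of the result?** At ICC 0.05 with t, Scenario 3, the upper limit is -1.98 + 0.947 = -1.03. Even at ICC 0.10 with a CV of 0.7, the half-width of about 1.25 leaves -1.98 + 1.25 = -0.73.

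**The case against.** **The size rests on an assumption.** This stands. No ICC appears in the documents, and nothing in them favours 0.05 over 0 or 0.01. At 0.01 the half-width grows by only about 0.04 on a 0–40 scale. A reader might infer that the interval will cover 85% or so. That needs an ICC near 0.05, which the documents do not supply.

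**Independence in the analysis is inferred from silence.** This also stands. A reader might infer that the SAP prescribes an independent-participant variance. It does not: it names no estimator. What can be said is that nothing in it accounts for site.

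**Much site variation cancels.** This largely stands. Stable differences in CAT level between hospitals drop out of a change from baseline, and the model also adjusts for baseline CAT. CAT is completed before other procedures and without knowledge of test results (Protocol 3.6.1.1). A reader might also cite Protocol 3.6.1.3, "All sites will use their own spirometry equipments for pulmonary function test". That has no bearing on CAT, and for FEV1 a stable device offset largely cancels as well. Only site variation in the change itself matters.

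**Sites could be regarded as fixed.** They are selected, not sampled, and the estimand defines a population of patients. On that view between-site variance does not enter the error in this way. But Protocol 3.3 wants the patients to be representative beyond the chosen hospitals, which favours counting it. A clustered standard error does not cure purposive selection, which Protocol 4 already lists as a limitation.

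**Precision is already stress-tested.** Table 4 gives 0.69–0.79 at SD 7.5, close to the range for ICC 0.01–0.02. That covers planning to a similar width, but for a different reason, and it does nothing for the reported interval.

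**Conclusion.** The point holds as one about precision. The range 0.64–0.73 is an independent-participant figure, and no part of the specified analysis allows for correlation within about 30 sites. If CAT change varies by site, the interval under-covers by an amount that the documents cannot settle: one to two percentage points at ICC 0.01, and six to eight at 0.05 with equal sites. If it does not vary, the stated figures are right.

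A reader might infer that the effectiveness conclusion is at risk. The documents do not support that: there is no test or success threshold, and a mean near -2 stays clear of zero across the range examined. This is a worthwhile, inexpensive improvement, not an error that invalidates the plan. It rests on SD 7, about 30 sites, the assumed ICCs, and inference that reaches beyond the selected sites.

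**What to change.** **SAP 4.2.2, and by reference 4.2.3, 4.3 and 4.4.** State the variance estimator. Take the standard error of each effectiveness mean or proportion from a site-clustered sandwich variance with small-sample correction, using t on (sites - 1) degrees of freedom. A bootstrap that resamples sites and refits the weights is an alternative. Report the observed ICC.

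**Protocol 3.7.2 and SAP 5.** Say that 0.64–0.73 assumes no site effect. Add the half-width over a range of assumed ICCs, computed with the same t reference as the analysis (the t column of the table), without singling out one ICC.

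**Cost.** No extra patients, visits or data are needed, since participants can be grouped by enrolling site. The interval widens by about 2–5% even if there is no site effect (the ratio of t to normal quantiles is 2.045/1.960 = 1.04). Some programming is needed: the clustered variance has to work in an observation-weighted MMRM and be combined by Rubin's rules over at least 1000 datasets, in the sensitivity analysis and wherever covariates are imputed.
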